9.3. Adjustment Criteria for Opioid Taper

Subjects will be tapered from their baseline total daily dose of opioid (calculated as MED) over a 14-day period. The opioid dose will be decreased as close as possible to achieve the following dose reduction targets: 50% from the baseline MED beginning with the last dose of the day on Day -1, an additional 25% of the baseline MED beginning with the first dose of the day on Day 6, and a final 25% of the baseline MED (to dose of zero) beginning with the first dose of the day on the day on Day 13 (Figure 1). Reminders for opioid dose reduction may be done via phone, text, or other electronic message.

Opioid dosing to achieve the required dose reductions in accordance with the protocol defined taper must be planned during Screening. Any changes in opioid prescription to facilitate the protocol taper should be discussed with the subject's primary pain physician, when applicable, and prescribed in advance of randomization. The Investigator should work with a preferred pharmacy informed about the subject's participation in a clinical trial in order to fulfill prescribing needs to facilitate the opioid taper. Opioid prescriptions should be written to accommodate the planned taper, based on the following considerations:

- Subjects should be maintained on the same opioid molecule throughout the taper and not converted to new molecules.
- Priority should be given to eliminating opioid medications for breakthrough pain as part of the first opioid dose reduction (50% of baseline MED) if possible. If not possible, dosing of opioid medications being taken for breakthrough pain should be

changed to be part of a fixed dose regimen appropriate to achieve the target MED reduction.

• Opioid dose reductions should be as close as possible to the nominal reductions specified per protocol (ie, 50% or 25% reduction). Round up on the dose of the available opioid formulation if unable to adjust exactly to meet nominal MED reduction criteria.

The subject's baseline opioid regimen and MED calculation as well as the opioid regimen planned to achieve each taper step should be submitted to and approved by the Medical Monitor prior to Day -1. The Investigator will discuss and confirm the subject's agreement to comply with the opioid dosing regimen for each opioid taper step based on the Medical Monitor-approved plan.

Non-opioid medications taken during the study should be in compliance with the allowed concomitant treatments in Section 9.4. Opioid dose reductions may not occur on a Friday or Saturday unless clinic can accommodate subjects on Saturday and Sunday. Qualified study personnel at the clinic should call the subject the day after the opioid dose is decreased (except on Day 1 since the subject will come to the clinic) to review the subject's at-home vital signs measurement and how the subject is feeling. Upon review by the Investigator or designee, changes to dosing of study drug should also be discussed with the subject, if applicable.

Subjects who experience intolerable withdrawal symptoms despite increasing their dose of study drug to the maximum tolerated dose (not to exceed 4 tablets QID) will be allowed to pause the opioid taper once. Pausing the opioid taper includes either a return to the last stable opioid dose for the remainder of the current opioid dose reduction period, or remaining on the current opioid dose instead of reducing at the next scheduled reduction, resulting in an overall extended opioid taper period and study duration. For example, if a subject experiences intolerable withdrawal at the second opioid dose reduction step [25% of baseline MED], they may either 1) return to the first reduction dose [50% of baseline MED]) or, 2) when the withdrawal persists until the next scheduled reduction step, they may remain for longer at the current opioid dose [25% of baseline MED]. In both cases, the taper must be resumed following the single pause in accordance with the protocol schedule. Subjects who cannot or are unwilling to continue the opioid taper after one pause will be discontinued from the study.

Decisions on whether to pause the opioid taper will be based on subject request and an evaluation (in clinic or over the phone) of the subject's status by the Investigator. Subjects may request to pause the opioid taper due to opioid withdrawal symptoms. If the subject's last COWS score is \geq 5 OR if based on i) the Investigator's discussion with the subject, ii) review of ongoing subject-reported withdrawal related AEs, and iii) most recent scores for subject reported withdrawal scales, the subject's desire to pause the taper is related primarily to opioid withdrawal discomfort in the Investigator's desire to pause the taper may be paused. In the event that the Investigator assesses the subject's desire to pause the taper to be primarily related to pain, a taper pause will not be permitted; however, if the subject is willing to continue the per protocol taper, recommended modifications to their concurrent pain management plan should be discussed and recorded. Subjects unwilling to continue the per protocol taper and not experiencing opioid withdrawal to permit a single pause should be discontinued from the study.

Study drug dosing for an opioid taper pause will remain at the discretion of the Investigator, as guided by subject tolerability of study drug and opioid withdrawal symptoms. The dose of study drug can be increased or decreased as needed.

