- ¹ Phone call will take place on Day 31, to check on the subject's well-being and to assess how the subject is feeling.
- ^m Phone calls will take place on Days 38, 45, and 52, to check on the subject's well-being and to assess how the subject is feeling.
- ⁿ Reminders contacts may be done via phone, text, or other electronic message. Remind the subjects about opioid dose reductions or, at Day 24, study drug dose reductions.
- ^o Opioid dose will be decreased 50% from baseline MED beginning with the last dose of the day on Day -1. The opioid dose will be decreased or maintained beginning on Day 6. The opioid dose will be decreased an additional 25% of baseline MED or maintained beginning on Day 13. A final 25% (to dose of zero) reduction will be made beginning on Day 19. Subjects who experience intolerable withdrawal symptoms despite increasing their dose of study drug to the maximum tolerated dose will be allowed to pause the opioid taper once. Pausing the opioid taper includes either a return to the last stable opioid dose for the remainder of the current opioid dose reduction period (eg, if a subject experiences intolerable withdrawal at the second reduction stage [25% of baseline MED], they can return to the first reduction dose [50% of baseline MED]), or remaining on the current opioid dose instead of reducing at the next scheduled reduction, resulting in an overall extended opioid taper period and study duration. In this scenario, a subject will taper to a dose of zero beginning on Day 19. Opioid dose reduction may not occur on a Friday or Saturday unless the clinic can accommodate subjects on Saturday and Sunday.
- ^p Detailed study drug dosing information can be found in Section 9.2.3. Study drug taper begins on Day 24.
- ^q Subject interview will be conducted via a centralized interviewer through a phone call. The interview should take place no more than 5 days after the EOS Visit.
- ^r Training includes when to call the site due to symptoms of hypertension or hypotension, or if the subject records a vital signs measurement that meets the criteria to contact the site.

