11.4. Subjective Opiate Withdrawal Scale of Handelsman (SOWS-H)

The SOWS-H scale assesses subjective symptoms of opioid withdrawal [Handelsman 1987]. It is a subject-rated scale consisting of 19 items that are scored on a 5-point scale of 0 = not at all, 1 = a little, 2 = moderately, 3 = quite a bit, and 4 = extremely. The overall score is the simple sum of the 19 item scores. Lower observed values in SOWS-H scores indicate a more positive clinical outcome. The SOWS-H will be completed daily beginning at Day 1 at home at bedtime and at clinic visits (and Early Termination, if applicable). The SOWS-H completed at the Day 1 Visit (Visit 1) should be completed prior to the first dose of study drug.

Item 16 of the SOWS-H was rephrased to be more appropriate for this population [FDA 2014].

A copy of the SOWS-H is provided in Section 16.6.

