12.1.2. Vital Signs

Orthostatic vital signs will be measured in-clinic. Orthostatic vital signs will be measured first after the subject has been sitting for at least 5 minutes (systolic/diastolic blood pressure, pulse, and temperature) and then after the subject has been standing for at least 3 minutes (systolic/diastolic blood pressure and pulse). On Day 1, orthostatic vital signs should be assessed pre-dose and 1-hour post-dose of study drug. A post-dose assessment is not required after Day 1. When repeat vital signs are performed, temperature does not need to be collected (only systolic/diastolic blood pressure and pulse).

Resting vital signs (systolic/diastolic blood pressure and pulse) only will be measured at home using a vital sign monitor during phone calls after dose reductions, and every day during the 4-day study drug taper through the EOS Visit. Resting vital signs will be measured after the subject has been sitting quietly for at least 5 minutes and, during the study drug taper and after, will be taken twice daily, once in the morning and once in the evening.

Subjects should contact the Investigator if they experience signs or symptoms of hypotension, bradycardia, or orthostasis (eg, lightheadedness, slow heart rate, dizziness, feeling faint at rest or when standing up) or hypertension (eg, pounding headache, dizziness, palpitations). Subjects should contact the Investigator if they record an at-home vital signs measurement reaching or exceeding a systolic blood pressure of ≥ 180 mmHg, diastolic blood pressure ≥ 105 mmHg, or heart rate of ≥ 120 bpm. Symptomatic episodes of hypotension should be captured as an AE. Confirmed instances of meeting criteria for hypertension should be captured as AEs regardless of symptomology.

During phone calls, the Investigator should ask the subject for a vital sign measurement and review subject-measured at-home vital signs.

Blood pressure and pulse measurements taken in-clinic or at-home should be repeated after a 15-30 minute rest if they meet the following criteria:

- Hypertension: systolic blood pressure of ≥180 mmHg, diastolic blood pressure ≥105 mmHg, or heart rate of ≥120 bpm
- Hypotension: systolic blood pressure of ≤90 or a diastolic blood pressure of ≤60, and a heart rate <50 bpm

If the subject has a confirmed systolic blood pressure of ≥ 180 mmHg, diastolic blood pressure ≥ 105 mmHg, or heart rate of ≥ 120 bpm, and is symptomatic, the subject should be seen (preferably by the Investigator).

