13.4.2.1.4. Vital Signs

Change from Baseline to each scheduled measurement will be summarized descriptively. Criteria to identify potentially clinically significant values will be defined in the Statistical Analysis plan.

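### The next-day call with home vital signs follows only an opioid decrease, so a pause that restores a higher opioid dose can pass with no scheduled blood pressure or pulse, chiefly in step 1

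*Combined protocol and SAP*

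**What the plan says.** Section 9.3 states that qualified site staff "should call the subject the day after the opioid dose is decreased (except on Day 1 since the subject will come to the clinic"). The call reviews home vital signs and how the subject feels, and any study drug change is then discussed. Sections 3.1 and 7.1 carry the same rule. Section 12.1.2 matches it: resting vital signs "will be measured at home using a vital sign monitor during phone calls after dose reductions", then daily from the study drug taper to the End of Study visit.

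Section 9.3 also allows one pause for intolerable withdrawal, after study drug has been raised to the maximum tolerated dose. The subject either holds the current opioid dose or makes a "return to the last stable opioid dose for the remainder of the current opioid dose reduction period". No call, visit or reading is attached to the return.

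In Table 3, the schedule for subjects who pause, vital signs before Day 24 are marked on Days 1, 2, 3, 7, 8, 14, 15, 20 and 21. Contacts on Days 5, 12 and 18 are dose reminders, possibly by text, without vital signs. Diary readings start on Day 24. For Day 6, Table 3 footnote o says "The opioid dose will be decreased or maintained beginning on Day 6"; later cuts fall on Days 13 and 19.

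**The concern.** Each of the four planned decreases has a reading the next day: Day -1 (Day 1 visit), Day 6 (Day 7 call), Day 13 (Day 14 call) and Day 19 (Day 20 call). The one permitted increase has none. The primary objective is safety and tolerability, and the synopsis rationale names hypotension and bradycardia among the signals to look for.

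Step 1 matters most. The first cut begins with the last dose on Day -1 and study drug begins on Day 1, so the planned taper never combines full baseline opioid with study drug. A step 1 return does, with study drug by then at the maximum tolerated dose. Section 8.4 warns that CNS depressants taken with lofexidine may raise the risk of hypotension and bradycardia. Counting opioids among those depressants is an assumption here; the protocol does not say so.

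The post-decrease call is also the scheduled prompt to revisit the study drug dose. After a return, a subject whose study drug was raised for withdrawal has no such call until after the next cut.

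**Working it through.** The plan gives no figure to reproduce. The check sets the Table 3 vital-sign days against the days a subject could spend at a restored dose.

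**Inputs.** The cuts on Days 6, 13 and 19 (Table 3 footnote o) bound three steps: Days 1-5, 6-12 and 13-18, or 5 + 7 + 6 = 18 possible return days. Readings within them fall on Days 1, 2, 3, 7, 8, 14 and 15. Clinic visits (Days 3, 8, 15) may move by one day (Section 7.1); calls are held at their stated days.

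**Return after the clinic visit, nominal days**

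| Step | Opioid level restored | Full days at that dose | Scheduled readings on them | Next reading | Days from visit |
|---|---|---|---|---|---|
| 1 | 100% of baseline | 4-5 | 0 | Day 7, after the Day 6 cut | 7 - 3 = 4 |
| 2 | 50% | 9-12 | 0 | Day 14, after the Day 13 cut | 14 - 8 = 6 |
| 3 | 25% | 16-18 | 0 | Day 20, after the Day 19 cut | 20 - 15 = 5 |

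**How many return days are uncovered.** A return day counts as covered if a reading follows the return within the same step.

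| Visit timing | Return on a visit day follows the visit | Return on a visit day precedes it |
|---|---|---|
| Nominal | Days 3-5, 8-12, 15-18: 12 of 18 | Days 4-5, 9-12, 16-18: 9 of 18 |
| All visits one day early | Days 2-5, 7-12, 14-18: 15 of 18 | Days 3-5, 8-12, 15-18: 12 of 18 |
| All visits one day late | Days 4-5, 9-12, 16-18: 9 of 18 | Days 5, 10-12, 17-18: 6 of 18 |

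Days 5, 10-12 and 17-18 are uncovered in every case. In step 1 alone the nominal count is 3 of 5 (Days 3-5), with a range of 1 to 4. These are counts of days, not of subjects.

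**Which levels are new on study drug.** The 50% level is read on Days 1-3 and the 25% level on Days 7-8, possibly at a lower study drug dose than at the pause. The 100% level is never read on study drug. Of the 12 nominal uncovered days, only Days 3-5 involve an opioid level not already observed.

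**Effect of the fix.** A next-day reading falls within the step for returns on Days 3, 4, 8-11 and 15-17, which is 2 + 4 + 3 = 9 of the 12. Returns on Days 5, 12 and 18 need a same-day reading, and 9 + 3 = 12.

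**The case against.** Several points on the other side stand.

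- The only worked example of a return is in step 2. Footnote o does not state a return to 100%, though nothing bars one.
- A pause requires study drug at the maximum tolerated dose. Section 9.2.3 gives 1 tablet per dose on Day 1, 2 (possibly 3) on Day 2, and discretion from Day 3. A return on Days 3-5 therefore needs quick escalation.
- The Investigator evaluates the subject before any pause, and a phone evaluation should include a reading (12.1.2). That reading precedes the return.
- Symptomatic subjects must call (9.5, 12.1.2), study drug may be lowered during a pause, and the DMC reviews cardiovascular events.
- The gaps are no longer than the intervals the schedule already accepts. What differs is that the opioid dose has been raised within the interval.

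A reader might infer three stronger claims that the documents do not support.

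- *All 12 nominal days carry equal weight.* They do not: in steps 2 and 3 the restored opioid level has already been read on study drug.
- *A low reading would go unnoticed, because subjects are told to contact the Investigator* "if they record an at-home vital signs measurement reaching or exceeding a systolic blood pressure of" *180 mmHg or other upper limits only.* Before Day 24, scheduled home readings are taken while staff are on the phone, and 12.1.2 requires a repeat when the low criteria are met.
- *Nothing is recorded at the restored dose.* Adverse events are still collected, and "The SOWS-H will be completed daily beginning at Day 1 at home at bedtime", as are SOWS-Gossop and MCGI-S. Only blood pressure and pulse are missing.

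The synopsis rationale ties its named signals to longer use of study drug. It does not single out an opioid increase on Days 3-5.

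**Conclusion.** The gap is real but narrow. A return to a higher opioid dose after the Day 3, 8 or 15 visit has no scheduled blood pressure or pulse at that dose before the next cut, and in step 1 this leaves the only combination of full baseline opioid with study drug unread. For steps 2 and 3 the concern is smaller. Holding the current dose, the other form of pause, is not affected.

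The conclusion rests on reading the text as allowing a step 1 return. The clinical weight rests on treating opioids as CNS depressants. The number of subjects cannot be estimated, because the documents give no pause rate, no split between the two forms of pause and no distribution of return days. This is a minor safety-monitoring improvement, worth making because it is cheap. It changes no endpoint, estimate or conclusion.

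**What to change.** In Sections 3.1, 7.1, 9.3 and 12.1.2, make the trigger the day after any change in opioid dose, including a return to the last stable dose, and use the call to review the study drug dose.

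- For a return on the last day of a step (Day 5, 12 or 18), the subject takes the home reading later that day, after the restored dose.
- The rule "Opioid dose reductions may not occur on a Friday or Saturday unless clinic can accommodate subjects on Saturday and Sunday" limits reductions, not returns, so a next-day reading can fall on an unstaffed weekend day. The subject then takes and records the reading at home and calls if it meets the low criteria already in 12.1.2 (systolic ≤90 or diastolic ≤60 mmHg, with heart rate <50 bpm).
- Show this as a conditional contact in Tables 3 and 5, and let the diary accept such a reading before Day 24.
- Section 13.4.2.1.4 says "Change from Baseline to each scheduled measurement will be summarized descriptively". Add a listing of these readings by treatment group, flagged as taken during a pause.

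The cost is wording, plus at most one extra call per returning subject, using the monitor already supplied. With one pause allowed and 60 subjects, the ceiling is 60 calls; the true number is unknown. On nominal visits, returns on Days 1, 2, 6, 7, 13 and 14 need no extra call because a reading is already due the next day. Home readings are resting, not orthostatic, and COWS at the restored dose would remain uncollected. The dosing and pause rules stay as they are.

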9.4. Prior and Concomitant Treatments

Prior treatments are defined as treatments taken within 30 days before randomization, regardless if usage continues after randomization. Concomitant treatments are defined as treatments taken after randomization.

Prior treatments will be documented on the eCRF. The reported treatments will be reviewed and approved by the Investigator/study physician/assigned staff for entry into the study.

All concomitant treatments will be recorded in subject diaries and on the eCRF along with dose, dates of administration, and reason for use.

9.4.1. Prohibited Treatments

The following treatments are not allowed within 30 days prior to Screening or throughout the study:

- Alpha-2 adrenergic agonists
- Antiarrhythmics
- Barbiturates
- Paraldehyde
- Stiripentol
- Psychoactive herbal preparations (including St. John's Wort, Kratom, cannabis, and products containing cannabinoids)
- Aspirin (baby aspirin permitted if taking prior to study for prophylactic purposes)

9.4.2. Permitted Treatments

Medications taken for stable hypertension are permitted when dose/regimen has been consistent for a minimum of 3 months prior to screening.

Strong cytochrome P450-2D6 inhibitors, muscle relaxants, benzodiazepines, hypnotics, soporifics, tricyclic antidepressants, selective serotonin reuptake inhibitors, permitted anticonvulsants (including but not limited to gabapentin and pregabalin) and medications given for stable neuro-psychiatric diagnoses at a consistent dose/regimen for at least 30 days prior to randomization are permitted in accordance with exclusion criterion 14. These medications must be continued at the same dose/regimen for the duration of the study drug administration period. In the event the subject reports new regular or chronic use of any of the above-mentioned medication (whether over-the-counter or prescription), eligibility to continue in the study must be evaluated in consultation with the Medical Monitor.

CNS depressants in combination with lofexidine may increase the risk of hypotension and bradycardia. Subjects should be advised to be cautious prior to driving or operating heavy

machinery if on concomitant benzodiazepines during the study until they know how they react to study drug.

Other concomitant treatments are permitted throughout the study, as clinically warranted, for the treatment of symptoms related to opioid withdrawal. The following treatments may be used in this study as appropriate:

- Guaifenesin (for cough).
- Alumina, magnesia, and simethicone (for emesis and nausea)
- Dioctyl sodium sulfosuccinate and psyllium hydrocolloid suspension (for constipation)
- Bismuth sulfate (Pepto-Bismol[®]) (for diarrhea)
- Diphenhydramine, melatonin and zolpidem (for insomnia)

Subjects taking a prescribed medication for opioid-induced constipation (OIC) prior to Screening may continue to use the medication on an as needed basis. Subjects should be advised to consider avoiding use of OIC medications during the opioid taper to not exacerbate withdrawal-induced diarrhea.

Use of concomitant treatments to treat withdrawal symptoms will be recorded daily by subjects using the diary.

Subjects experiencing pain requiring medication will be allowed to use the following treatments:

- Acetaminophen (up to 4 g per day, dispensed as 500-mg tablets). Subjects receiving acetaminophen-containing opioid products should not receive acetaminophen as part of their pain management plan.
- Nonsteroidal anti-inflammatory drugs provided dosing is within product label recommendations
- Non-opioid topical treatments (compounded or non-compounded)
- Non-prescription medications that are often taken to treat pain, depression and anxiety (excluding St. John's Wort, Kratom, cannabis and products containing cannabinoids)
- Non-pharmacologic modalities/interventions (eg, physical therapy, psychotherapy, hypnosis, acupuncture, massage, chiropracty, ice packs, moist or dry heat, etc)

Use of opioid medication as a rescue for breakthrough pain should be strongly discouraged. Subjects experiencing intolerable pain during the study should be instructed to call the site to discuss further modifications to their non-opioid pain management plan. Subject reported use of any opioid rescue medication should be recorded and discussed by the Investigator and Medical Monitor to assess eligibility to continue in the study and will include a review of safety concerns, impact on effectiveness measures, and consistency with required MED-percent reduction targets. More than 2 repeat occurrences of opioid rescue medication usage reported by the subject will require study discontinuation.

Use of any medication or non-pharmacologic intervention or treatment for pain will be recorded daily by subjects using the diary.

